7.2 Visit Description

If not stated otherwise, the examinations listed in the following sections will be performed by, or under the supervision of, an investigator or a qualified delegate.

Unscheduled visits may occur as necessary, when clinically indicated at the investigator's discretion. Relevant and clinically significant laboratory data and AEs obtained at the unscheduled visits should be entered into the eCRF and recorded in the source documentation as necessary.

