5.3.2 Dose Modifications for HEMATOLOGIC Toxicities

For cycle 2 and beyond, Day 1 administration of PCLX-001 requires a platelet count of $\geq 75 \times 10^9/L$ and an absolute neutrophil count (ANC) of $\geq 1.5 \times 10^9/L$. CBC's drawn within 72 hours of treatment day may be used provided they meet parameters. However, if treatment parameters are not met, dose interruption will be made on the basis of blood counts taken the day of scheduled treatment. If counts are below this threshold, treatment will be delayed for 1 week and reassessed weekly until these parameters are met.

If a patient experiences a hematologic DLT in the preceding cycle OR if treatment is held for > 7 days due to neutropenia and/or thrombocytopenia, then the subsequent cycle will be administered at one lower dosing level. No more than two dose reductions will be allowed.

Patients should not receive prophylactic G-CSF for cycle 1. Subsequent use will be at the discretion of the treating physician and as per the ASCO guidelines on colony stimulating factors.

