- b. If a patient discontinues study treatment at any time during the study for any reason (except for patients who died, withdrew consent and objected to further data collection, or were lost to FU), an active FU assessment should be performed 30 days (± 4 days) after the last dose of the last study drug.
- c. Prescribed and OTC.
- d. Questioning for AEs will be conducted at clinic visits; in addition, spontaneous reports of AEs will be collected throughout the study.
- e. PK sampling: For patients in dose escalation, see Table 7C for schedule. For patients in dose expansion, see Table 7D for schedule.
- f. To be taken pre-dose of each cycle Day 1 within 60 min before the morning dose and EOT
- g. Hematology includes CBC + differential (i.e. hemoglobin erythrocytes, leukocytes, platelets, MCV, RDW, hematocrit, neutrophils, lymphocytes, monocytes, eosinophils, basophils, immature granulocytes, nucleated RBCs). Detection of CTCAE Grade 4 neutropenia (only Cycle 1) will trigger twice-weekly white blood cell counts to be performed, so that DLT determination can be made.
- h. Blood chemistry includes: sodium, potassium, chloride, bicarbonate or total CO² (as per site practice), calcium, phosphate, magnesium, total protein, albumin, glucose, serum creatinine, urea, uric acid, total bilirubin, ALT, AST, LDH, alkaline phosphatase, lipase.
- i. Window for tumour assessment is ± 5 days from Day 28 of the even-numbered cycles. CT of the relevant disease region for solid tumors and CT thorax, abdomen, pelvis \pm neck for NHL.
- j. Women of childbearing potential (including women of childbearing potential whose partners are sterilized) must have a negative pregnancy test.
- k. This scan should only be performed for NHL patients and is optional (i.e. not required for patients with other histologies). If a PET-CT is performed at screening, it should be repeated once after the sixth cycle if no progressive disease is detected during the course of treatment and / or to confirm complete response or disease progression.
- l. Exam to be symptom-directed.
- m. To be performed if clinically indicated (e.g. positive HBsAg and/or anti-HCV tests as performed during screening).
- n. Unless otherwise indicated, the window for visits is ± 2 days.
- o. Electronic records will be used to assess patient survival monthly (± 1 week) from the date of the follow-up visit.

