9. ADVERSE EVENT REPORTING

9.1 Definition of an Adverse Event

Any untoward medical occurrence in a patient or clinical investigation subject administered a pharmaceutical product and which does not necessarily have a causal relationship with this treatment. An adverse event (AE) can therefore be any unfavourable and unintended sign (including a clinically significant abnormal laboratory finding), symptom, or disease temporally associated with the use of a medicinal (investigational) product, whether or not related to the medicinal (investigational) product.

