9.2 Reporting, Recording and Follow-up of Adverse Events

This study will use the International Common Terminology Criteria for Adverse Events (CTCAE), version 5.0, for adverse event reporting.

For all AEs, relationship to study drug will be reported on the appropriate AE eCRF page. The PI must judge whether the study drug caused or contributed to the AE in which case it is considered to be an adverse drug reaction, and report it as either:

Related (definitely, probably or possibly): there is a reasonable possibility that the study drug caused or contributed to the AE; this conclusion may be supported by the following observations, though these are not required for the determination of relatedness:

- There is a plausible time sequence between onset of the AE and study drug administration;
- There is a plausible biological mechanism through which study drug may have caused or contributed to the AE;

Not related: It is highly unlikely or impossible that the study drug caused or contributed to the AE; this conclusion may be supported by the following observations, though these are not required for a determination of not related:

- another cause of the AE is evident and most plausible;
- the temporal sequence is inconsistent between the onset of the AE and study drug administration; a causal relationship is considered biologically implausible.

All AEs and SAEs occurring after initiation of study drug, regardless of relationship to intervention, will be reported from time of first dose until 30 days after the last dose of study drug or until the initiation of another anti-cancer therapy, whichever occurs first. After this period, investigators should report any serious adverse events that the investigator believes have at least a reasonable possibility of being related to the investigational product.

The investigator should follow each adverse event until the event has resolved to baseline grade or better or is assessed as stable by the investigator or until the patient is lost to follow-up or withdraws consent. Every effort should be made to follow all serious adverse events considered related to study drug or study-related procedures until a final outcome can be reported.

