During the study period, resolution of adverse events (with dates) should be documented on the Adverse Event electronic Case Report Form (eCRF) and in the patient's medical record to facilitate source data verification. If, after follow-up, return to baseline status or stabilization cannot be established, an explanation should be recorded on the Adverse Event eCRF.

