9.3.1 SAE Reporting

All SAEs defined as per ICH guidelines and other adverse events must be recorded on case report forms. In addition, all serious adverse events must be reported by using the SAE form and must be submitted to Ozmosis Research Inc.

Serious Adverse Event Reporting Instructions

All serious adverse events must be reported as follows:

Within 24 hours: Report initial information (on trial specific SAE report form) by fax to:

Ozmosis Research Inc.

[contact]

[contact]

The initial information should always contain:

- Name of Reporter/Investigator,
- Subject Identification,
- Adverse Event Term,
- Study Drug Dose and Start/Stop Dates

On the next working day: Fax completed trial-specific Serious Adverse Event form

All follow-up SAE reports should be submitted to Ozmosis as soon as possible.

The PI/Sponsor will be made aware of all Serious Adverse Events within 24 hours. All SAEs will be reported to the local research ethics board (REB) and regulatory authorities, as applicable, in accordance with local guidelines. Health Canada, any collaborating centres and any pharmacovigilance teams (as applicable) will be notified by the Sponsor in an expedited manner of all SAEs which are unexpected and related to the investigational product.

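### Section 7.2 lets investigator judgement decide which unscheduled laboratory values reach the eCRF, so worst laboratory grade can be understated, mainly from Cycle 2 onward and in Part B

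*Combined protocol and SAP*

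**What the plan says.** Section 7.2 (Visit Description) allows unscheduled visits when clinically indicated, at the investigator's discretion. On the data they produce it says: "Relevant and clinically significant laboratory data and AEs obtained at the unscheduled visits should be entered into the eCRF". Neither criterion in that sentence is defined.

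Four other places bear on the same data:

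- **Section 9.1** defines an AE as any unfavourable sign, "including a clinically significant abnormal laboratory finding".
- **Section 9.2** says: "All AEs and SAEs occurring after initiation of study drug, regardless of relationship to intervention, will be reported from time of first dose". It adds: "For all AEs, relationship to study drug will be reported on the appropriate AE eCRF page". Section 9.3.1 repeats the point: "All SAEs defined as per ICH guidelines and other adverse events must be recorded on case report forms".
- **Table 7B, footnote g** covers Grade 4 neutropenia in Cycle 1, which "will trigger twice-weekly white blood cell counts to be performed, so that DLT determination can be made". **Section 5.3.2** covers low counts on Day 1 from Cycle 2 onward: "treatment will be delayed for 1 week and reassessed weekly until these parameters are met". Neither set of repeat counts has a column in Table 7B.
- **Section 11.2** requires the hematology and biochemistry eCRF section, with source laboratory reports, within 7 working days of each Part A patient completing Cycle 1.

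Section 8.4 plans descriptive statistics for toxicity. It gives no rule on whether unscheduled values count toward worst grade.

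**The concern.** A laboratory table is normally read as the worst value each patient had. Here, a value found between scheduled visits is asked for only if someone at the site has already judged it important. Capture therefore depends on the result, and on who assesses it. Two sites could see the same count and leave different records.

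The AE form does not clearly fill the gap, because section 9.1 applies the same test of clinical significance. One judgement can thus keep a value out of both records, and the eCRF would then hold nothing from which to check that judgement.

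Safety and tolerability is a primary objective (section 2). Section 3.5 bases the recommended Phase II dose on data from all parts and stages of the study, including the intensity of AEs. Section 3.2 asks for cumulative toxicity in later cycles to be watched. Later cycles and Part B are also where the protocol offers the least other protection for these values.

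**Working it through.** The plan states no figure on this point, so there is none to reproduce. The check has two parts.

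**1. Following one value through the text.** Take a Grade 3-4 laboratory value from an unscheduled visit that the investigator judges not clinically significant.

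- *Laboratory record:* section 7.2 asks for significant values and sets no requirement for the others.
- *AE record:* section 9.1 names laboratory findings as AEs when they are clinically significant. This one was judged not to be, so the all-AE rule in 9.2 need not catch it.
- *Part A Cycle 1:* section 11.2 brings in the laboratory eCRF section and the source reports, so the value can be seen at cohort review.
- *Cycle 2 onward, and Part B in any cycle:* section 11.2 does not apply, and no other entry rule for such values was found.

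**2. How much scheduled testing would catch instead.** Table 7B schedules hematology on Days 1, 8, 15 and 22 of Cycle 1, Days 1 and 15 of Cycle 2, and Day 1 of each later cycle. In study days these are 1, 8, 15, 22, 29, 43, 57, 85 and so on. The chemistry row has the same marks. With a visit window of ±2 days (footnote n), the longest gap is the nominal gap plus 2 + 2 = 4 days.

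Let an episode last L days and scheduled counts be g days apart. If onset is uniform over the interval, the probability that at least one scheduled count falls within the episode is min(1, L/g).

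| Period | Gap g (days) | Longest gap with windows | L = 7 | L = 4 |
|---|---|---|---|---|
| Cycle 1 | 7 | 7 + 4 = 11 | 7/7 = 100% | 4/7 = 57% |
| Cycle 2 | 14 | 14 + 4 = 18 | 7/14 = 50% | 4/14 = 29% |
| Cycle 3 onward | 28 | 28 + 4 = 32 | 7/28 = 25% | 4/28 = 14% |

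The gaps come from Table 7B. Uniform onset and the lengths of 7 and 4 days are illustrative assumptions, and the probabilities use the nominal gaps. On these assumptions, scheduled tests from Cycle 3 onward would miss 75% of 7-day episodes and 86% of 4-day episodes. Any record of those would have to come from an unscheduled or repeat value, or from an AE entry.

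**The AE wording.** In the section 7.2 sentence the qualifier stands before both laboratory data and AEs. If it governs only laboratory data, sections 7.2 and 9.2 agree. If it governs both, 7.2 asks for a subset of AEs while 9.2 and 9.3.1 ask for all of them. The sentence permits either reading.

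**The case against.** The strongest reply is that section 7.2 is loosely worded but that other rules contain its effect. Much of this stands, and it rules out several stronger readings.

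- **A reader might infer that other results are barred from the eCRF.** The text does not say so. It states what should be entered and is silent on the rest. A site may enter everything, and a repeat count during a severe cytopenia could well be judged relevant.
- **A reader might infer that the safety database is left without the repeat counts.** The documents do not support this. The recounts in footnote g and section 5.3.2 are protocol-mandated, whereas section 7.2 describes visits at the investigator's discretion. Nothing calls the recounts unscheduled. In Part A Cycle 1, where the 7-day neutropenia criterion of section 3.2 applies, section 11.2 secures the laboratory pages and source reports. What remains is that, outside that setting, the recounts have no explicit entry rule.
- **A reader might infer from the 28-day spacing that one missing value stretches a recorded event by about four weeks.** Section 9.2 puts resolution dates for recorded AEs on the AE form. Section 5.5 transfers each dose interruption to the eCRF. Under section 5.3.2, the count that ends a hold at the start of a cycle also qualifies the patient for Day 1, where hematology is scheduled. Duration of a recorded AE therefore does not rest on the spacing of laboratory rows.
- **A reader might infer a flat contradiction with section 9.2.** It is an ambiguity, and it concerns AEs only. For laboratory values, sections 7.2 and 9.1 apply the same standard.

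It can also be said that section 8.4 defines no worst-laboratory-grade table, so no specified analysis is biased. That is correct as far as it goes, but any summary of laboratory toxicity would use whatever values were entered. None of these replies reaches an unscheduled value judged not significant in Cycle 2 or later, or in Part B.

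**Conclusion.** The point holds in a limited form. Section 7.2 makes the capture of unscheduled laboratory values depend on investigator judgement, and section 9.1 uses the same judgement for AE status. A Grade 3-4 value judged not significant can therefore be missing from both records. The exposure is mainly Cycle 2 onward and Part B. After Cycle 1, scheduled hematology is 14 and then 28 days apart. In Part B Cycle 1 it is still weekly, but the section 11.2 submission does not apply.

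The likely direction is an understated worst laboratory grade. The amount cannot be calculated, because it depends on how often sites take unscheduled samples and how they judge the results, and the documents give neither. The detection probabilities show only how little scheduled testing can substitute after Cycle 1. They are not an estimate of bias.

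The possible inconsistency with section 9.2 is secondary and depends on how one sentence is parsed. This is an inexpensive improvement to data supporting a primary objective, not a flaw that puts the study's conclusions in doubt.

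**What to change.** Replace the section 7.2 sentence with:

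*All AEs, and all hematology and chemistry results obtained at unscheduled visits or as protocol-required repeat counts (5.3.2; Table 7B footnote g), are entered in the eCRF with dates, whatever their clinical significance.*

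This settles the AE ambiguity and gives the repeat counts an explicit entry rule, whether or not they count as unscheduled.

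Add to section 8.4 that worst laboratory grade is derived from scheduled plus unscheduled values.

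The cost is data entry. No test or visit is added. Reported laboratory toxicity rates may be slightly less favourable, because values that could now be left out would be counted.

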7.2.1 Screening

Pre-study examinations will be performed within 28 days before first administration of PCLX-001.

Because some patients may not satisfy all inclusion and exclusion criteria, more patients than the pre-specified number of evaluable patients will be screened. As soon as fulfillment of all criteria is confirmed by the investigator, the patient will be allowed to enter the treatment phase of the study.

A signed written informed consent form (ICF) will be obtained before any general screening procedure for the study may begin.

7.2.2 Treatment Visits

At each visit, laboratory investigations and/or measures and action will be as per the Schedule of Evaluations (Tables 7A and 7B).

7.2.3 Follow-Up Visits

If a patient discontinues study drug at any time during the study for any reason (except for patients who died, withdrew consent and objected to further data collection, or were lost to FU), an active FU assessment should be performed 30 days (\pm 4 days) after the last dose of the last study drug (Table 7B).

Long-term follow up will occur monthly to assess patient survival only. Patients will not be contacted for these visits; electronic records will be reviewed to complete the assessments.

7.2.4 End of Treatment Visit

If a patient discontinues the study for any reason except death, withdrawal of consent and objection to further data collection, loss to FU, or extended treatment interruption, an EOT evaluation should be performed as soon as possible after the last dose of the study drug, but always within 30 days (\pm 4 days) after the last dose of study drug.

The EOT visit should be performed as a clinic visit (except for patients who died, withdrew consent and objected to further data collection, or were lost to FU).

The assessments to be performed at the EOT visit are described in the Schedule of Evaluations (Table 7B).

7.3 Determination of Efficacy Outcomes

Tumor response and progression of solid tumors and NHL will be evaluated by the investigator at each study center consistent with RECIST 1.1 criteria (see [Appendix B](#)), or Lugano Classification of Lymphoma response (see [Appendix C](#)).

Tumor markers can play a role in detecting disease and assessing response to therapy in selected groups of patients. In monitoring patients for disease progression, tumor marker levels should be determined according to clinical practice (e.g., CA125 for ovarian cancer, CEA for colorectal cancer, PSA for prostate cancer).

Solid Tumors

In *measurable* lesions (i.e. at the primary site, visceral [≥ 1.0 cm long axis], or nodal [in lymph nodes ≥ 1.5 cm short axis] lesions), the objective response will be assessed by contrast-enhanced CT or MRI and documented consistent with RECIST 1.1 criteria (see [Appendix B](#)). Tumor measurements for efficacy evaluation will be made every 2 cycles, beginning with a baseline scan and unless progression is noted, all lesions will be assessed and reported at the end of every second cycle, starting at the end of Cycle 2.

Non-Hodgkin's Lymphoma

Efficacy will be assessed based on radiological tumor evaluations, which will include neck, chest, abdomen, and pelvis by contrast-enhanced CT / MRI scans. PET-CT can be utilized throughout the study if it is considered standard of care at the institution. Scans will be performed as shown in Table 7A and Table 7B and will be evaluated locally at the study site.

PET-CT is optional in this study and should be done based on institutional standards whereas the CT portion of the PET-CT should be of diagnostic quality, i.e. appropriate radiation dose and contrast enhancement. In case the CT portion of the PET-CT is performed for attenuation correction only an additional whole body CT in diagnostic quality is needed. If a PET-CT with a PET positive finding was performed at screening an interim PET-CT should be done after the sixth cycle. For any imaging follow-up after interim PET-CT it is recommended to confirm any changes in previous metabolic overall response that were assessed with CT alone with PET-CT.

Response assessment will be based on the Lugano Classification (see [Appendix C](#)).

7.4 Pharmacokinetics

7.4.1 Drug Measurements

In patients enrolled in Part A dose escalation, serial blood (plasma) samples will be collected at the time points shown in Table 7C to assess PK of PCLX-001. For patients enrolled in Part B dose expansion, serial blood (plasma) samples will be collected at the pre-dose time points shown in Table 7D.

Whenever possible, all efforts should be made to adhere to the blood-sampling schedules given in Tables 7C and 7D. However, based on practical considerations, the following time ranges are provided as guidance:

Pre-dose samples should be collected within 15 min before the administration of PCLX-001. For 0.5 hours post dose, the PK sample should be collected within \pm 6 minutes. Subsequent PK samples should be collected \pm 15 minutes of planned time point. Sampling times outside these suggested intervals will not be considered as protocol deviations. The date and time of actual blood sampling and dose administration will have to be documented in the eCRF because PK calculations will be based on the actual sampling times relative to dosing times.

Cumulated substantial deviations of sampling times and / or consecutive, missing PK samples may lead to an insufficient (inadequate) description of the plasma concentration vs. time profiles of PCLX-001, and thus affect the quality of the PK evaluation of the respective patient(s). In this case, these deviations should be classified as “important” and may lead as declared “validity findings” to the exclusion of the respective patient(s) from the PK analysis set.

Details on sampling procedures, sample storage, and shipment are documented in separate sample handling documentation.

Table 7C: Schedule of pharmacokinetic blood sampling time points in Part A Dose Escalation

Procedures	Study Treatment Period 1 Cycle = 28 days								
	Cycle 1					Cycle 2		Cycle 3/ Beyond	EOT Visit
Visit Identifier (Visit Window)	Day 1	Day 2	Day 8 (±2)	Day 15 (±2)	Day 22 (±2)	Day 1 (± 2)	Day 15 (±2)	Day 1 (±2)	
	X	X	X	X	X	X	X	X	X
Pharmacokinetics									
Pre-dose* (-15 min)	X	X	X	X	X	X	X	X	X
0.5 hour (± 6 min)	X			X					
1 hours (± 15 min)	X			X					
2 hours (± 15 min)	X			X					
4 hours (± 15 min)	X			X					
8 hours (± 15 min)	X			X					

*If patient is receiving a dose on that day

Table 7D: Schedule of pharmacokinetic blood sampling time points in Part B Dose Expansion

Procedures	Study Treatment Period 1 Cycle = 28 days								
	Cycle 1					Cycle 2		Cycle 3/ Beyond	EOT Visit
Visit Identifier (Visit Window)	Day 1	Day 2	Day 8 (±2)	Day 15 (±2)	Day 22 (±2)	Day 1 (± 2)	Day 15 (±2)	Day 1 (±2)	
	X			X		X		X	
Pharmacokinetics									
Pre-dose* (-15 min)	X			X		X		X	

*If patient is receiving a dose on that day

